- Correlation between postprandial changes in the oxygenated/deoxygenated hemoglobin signal in the wall of the gastrointestinal tract measured by MSOT and postprandial changes in Doppler sonographic signals in the large arteries of the splanchnic artery.
- Comparison of the ICG signal in the lumen of the gastrointestinal tract measured by MSOT between fasting subjects, subjects after ingestion of food and subjects after ingestion of food containing ICG.
- Measurement of the postprandial change in the ICG signal in the lumen of the gastrointestinal tract measured by MSOT over time and over the different sections of the gastrointestinal tract in subjects after ingestion of food containing ICG.
- Correlation between postprandial changes in the oxygenated/deoxygenated hemoglobin signal in the wall of the gastrointestinal tract measured by MSOT and postprandial changes in the ICG signal in the lumen of the gastrointestinal tract measured by MSOT in subjects after ingestion ICG-containing food.

Study type

Since no data exist to support the hypothesis of this study to date, it is an exploratory study.

6. Target parameters

Study related measures and target
All MSOT measurements are taken over the gastric antrum, terminal ileum, transverse colon, and sigmoid colon.
Primary targets (obligatory):
Quantitative de-/oxygenated hemoglobin signal (in arbitrary units)
These target values are collected non-invasively using MSOT.
Secondary targets:
Qualitative and quantitative ICG signal (in arbitrary units)
Quantitative single wavelengths signal (in arbitrary units)
Optoacoustic spectrum (in arbitrary units, normalized)
These target values are collected non-invasively using MSOT.
Secondary targets (optional):
Doppler sonographic signals of the coeliac trunk, superior mesenteric artery, inferior mesenteric artery:

• Doppler sonographic spectrum• Doppler sonographic curve• Velocity profile• Flow profile• Flow volume• Resistance index• Pulsatility index
These target values are collected non-invasively using sonography.

7. Study design

Monocentric / multicentric

It is a monocentric diagnostic study with prospective data collection (Investigator Initiated Trial, IIT).

Study arms:

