A comparison is made between 3 study arms: A: Fasting, B: Standardised breakfast, C: Standardised breakfast with added ICG (250mg in 50ml aqua). As part of the crossover design, each subject will pass through all three study arms on three different days. There is a period of at least 48 hours between two consecutive study days for each subject.

Randomisation

Randomisation is not planned. As part of the crossover design, each subject passes through all three study arms. The order of the study arms is identical for each subject:

1. Study arm A: Fasting
2. Study arm B: Standardised breakfast
3. Study arm C: Standardised breakfast with added ICG

Blinding

No blinding is planned.

8. Study population

Inclusion and exclusion criteria

Inclusion criteria:

- Age over 18 years
- Written declaration of consent

Exclusion criteria

Generally valid:

- Pregnancy
- Nursing mothers
- Tattoo in the field of investigation
- Subcutaneous fat tissue over 3 cm
- Chronic or acute diseases of the gastrointestinal tract or symptoms suggestive of such a disease
- Diseases requiring acute treatment
- Lack of written consent

ICG related:

- Known hypersensitivity to ICG, sodium iodide or iodine
- Hyperthyroidism, focal or diffuse thyroid autonomy
- Treatment with radioactive iodine for the diagnostic examination of thyroid function within two weeks before or after the study
- Restricted renal function
- Intake of the following drugs: Beta-blockers, anticonvulsants, cyclopropane, bisulphite compounds, haloperidol, heroin, meperidine, metamizole, methadone, morphine, nitrofurantoin, opium alkaloids, phenobarbital, phenylbutazone, probenecid, rifamycin, any injection containing sodium bisulphite.

Subject number

As this is a pilot study, it is not possible to calculate the exact number of cases. It is planned to examine a total of 10 study subjects.

Recruitment measures

Volunteers will be informed by means of a public notice and via the homepage of the University Hospital Erlangen. If volunteers are willing to participate, they will be fully informed about the aims and methods (especially about the scientific/explorative nature of the study), the benefits and risks and the revocability of participation in the study. Each participant receives an expense allowance of 150€.

9. Study course

Procedure for informing about and obtaining consent

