The study starts for the participants at 10 pm on the day before the first examination day with adherence to the fasting period. On the first examination day, the preprandial measurement is performed at 8 am after 10 hours of fasting in all study arms. The preprandial measurement starts with the sonographic localisation of the sections of the gastrointestinal tract that will be examined in the following measurements with MSOT and Doppler sonography. Skin markings are made with a skin-compatible marker pen for better reproducibility of the following measurements. The further procedure of the preprandial measurement and each of the following postprandial measurements will follow an identical measurement protocol. A period of 20 minutes is planned for each measurement protocol. Depending on the study arm, the subjects remain fasting throughout all the measurements of the day (study arm A) or receive a standardised breakfast with or without ICG supplement (study arm B/C) 30 minutes after the start of the preprandial measurement. After the subjects have eaten the breakfast within 15 minutes, the first postprandial measurement takes place exactly 60 minutes after the preprandial measurement in all study arms. In the following 6 hours, further postprandial measurements are taken at 60-minute intervals, so that the last measurement takes place exactly 7 hours after the start of the preprandial measurement. 4 hours after breakfast, the subjects from study arms B and C receive another standardised meal to simulate regular food intake. This meal does not contain ICG. The subjects in study arm A remain fasting throughout all the measurements of the day.

On each measurement day two subjects are examined in parallel with a time offset of 30 minutes. This means that the entire examination for the second participant begins at 8:30 am.

[figure not shown]

Figure 1: Course of one examination day for one participant. X-axis is time in minutes with 0 being the beginning of the preprandial measurement at 8:00 or 8:30 am..

In a crossover design, each participant is examined on three measurement days according to the three study arms. There must be a minimum time interval of 48 hours between each examination day for the participant. The order of the examination days is predetermined:

1st examination day (study arm A): Fasting

2nd examination day (study arm B): Standardised breakfast

3rd examination day (study arm C): Standardised breakfast with ICG

[figure not shown]

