Figure 3: Flowchart

Measurement protocol

At the beginning of the preprandial measurement, the sections of the gastrointestinal tract that are to be examined in the following measurements with MSOT and Doppler sonography are localised sonographically and markings are made on the skin surface with skin-compatible marker in order to achieve better reproducibility over the following measurements.

The further procedure of the preprandial measurement and each of the following postprandial measurements are carried out according to a identical measurement protocol.

Optoakustische Messungen

- a. Magenantrum
- b. Terminales Ileum
- c. Colon transversum
- d. Colon sigmoideum

2. Doppler-sonographische Messungen
 - a. Truncus coeliacus
 - b. Arteria mesenterica superior
 - c. Arteria mesenterica inferior

The estimated time for a complete measurement according to the protocol is 20 minutes.

At the beginning of each measurement, each subject drinks 150ml of still mineral water in order to achieve a uniform filling of the stomach during the optoacoustic measurement of the gastric antrum.

Composition of the standardised breakfast and meal

The composition of the standardised continental breakfast and the standardised meal are identical and take into account the gender and body weight of the participant. With an energy content of 400-700 kcal (8.2 kcal/kg bw), the meal each accounts for about 25% of the daily energy requirement. The nutrient composition is 55% carbohydrates, 29% fat and 16% proteins.

Woman	Man
60 kg	80 kg
500 kcal	650 kcal
1½ multigrain bread roll	
1 portion of jam	
½ cream cheese, lean	
½ portion of butter 1 slice of cheese (Emmental or Maasdam)	1 portion of butter 1 slice of cheese
< 65 kg: up to 2x 200 ml water >65 kg, < 70kg: 100 ml orange juice up to 2x 200 ml water >70 kg: 200 ml orange juice up to 2x 200 ml water	<85 kg: 200 ml orange juice up to 2x 200 ml water >85 kg: 300ml orange juice up to 2x 200 ml water

Study participants in study arm C drink 250mg of ICG (Verdye, Diagnostic Green) dissolved in 50ml of water with the standardised breakfast.

Total duration of the study

The estimated total duration of the study until the inclusion of the last participant is approximately 12 months.

Risk-benefit analysis

Study-related risks of MSOT

Based on the classification criteria for medical devices (Directive 93/42/EEC, Annex IX), the optoacoustic system of iThera Medical corresponds to Class IIa:

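### The 150 ml of water standardises added volume, not gastric filling, so an antral fed–fasting difference soon after a meal cannot be attributed to blood flow alone

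*Combined protocol and SAP*

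**What the plan says.** Section 9, Measurement protocol, sets the control for the antral reading: "At the beginning of each measurement, each subject drinks 150ml of still mineral water in order to achieve a uniform filling of the stomach". It applies to every reading in every arm.

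The arms differ in what else is swallowed (Section 9, Time schedule):

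- Arm A: "The subjects in study arm A remain fasting throughout all the measurements of the day".
- Arms B and C: breakfast is given "30 minutes after the start of the preprandial measurement". The plan continues: "After the subjects have eaten the breakfast within 15 minutes, the first postprandial measurement takes place exactly 60 minutes after the preprandial measurement".
- Later the same day: "4 hours after breakfast, the subjects from study arms B and C receive another standardised meal to simulate regular food intake".

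Meal size is given under the composition of the breakfast: "With an energy content of 400-700 kcal (8.2 kcal/kg bw), the meal each accounts for about 25% of the daily energy requirement". Drinks are scaled by sex and weight, and arm C takes a further 50 ml of water with the dye at breakfast.

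The primary target in Section 6 is "Quantitative de-/oxygenated hemoglobin signal (in arbitrary units", measured at the antrum and three other bowel sites. Neither Section 6 nor Section 10 lists wall depth, wall thickness, luminal size, a depth correction or a depth covariate. Probe position is controlled by skin marks made at the preprandial reading. The only item that may relate to depth is an entry exclusion, "Subcutaneous fat tissue over 3 cm", for which no reason is given.

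**The concern.** By giving water to even out filling, the plan treats filling as something that can affect the antral reading. An equal volume can even out filling among readings in the fasting arm. It cannot do so between a stomach that has just received a meal and one that has not, and that is the contrast in the primary objective (Section 5).

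If a fuller stomach places the antral wall at a different distance from the probe, the recorded signal could change without any change in perfusion. Skin marks fix the probe, not the wall beneath it. Subtracting the same-day preprandial value would not help, because filling changes after that reading.

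The attribution to blood flow is at stake. Section 5 sets out to characterise blood flow in the wall, and Section 4 expects gastric hyperaemia 30 to 60 minutes after eating, which is when the meal is in the stomach. The antrum is also the most oral of the four sites, so it is the starting point for the hypothesis that changes run from oral to aboral.

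**Working it through.** **1. Timing (Section 9, Time schedule).** Readings are at 0, 60, …, 420 min, 8 in all, so the water totals 8 × 150 = 1200 ml per day in each arm. Breakfast runs from 30 to at most 45 min. The reading at 60 min is therefore 60 − 45 = 15 min after the meal ends. Counted from the start of breakfast, the second meal is at 30 + 240 = 270 min, and the next reading, at 300 min, is 30 min later.

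**2. Meal size (Section 9, composition).** Check on the energy figures: 8.2 × 60 = 492 kcal and 8.2 × 80 = 656 kcal, matching the stated 500 and 650 kcal. These are whole-meal totals for two example weights within the 400–700 kcal range. Drinks per meal (juice plus 0 to 400 ml of optional water):

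- women under 65 kg: 0–400 ml
- women 65–70 kg: 100–500 ml
- women over 70 kg: 200–600 ml
- men under 85 kg: 200–600 ml
- men over 85 kg: 300–700 ml

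Solids come on top. Arm C adds 50 ml at breakfast.

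**3. What the water does to the contrast.** Let W(t) be residual water and M(t) residual meal. Treating W as equal in the arms, fed minus fasting content = [W(t) + M(t)] − W(t) = M(t). The water cancels, whatever its volume.

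**4. Size of M(t), on assumptions.** The documents give neither total meal volume nor emptying rate. Assume volume V of 300, 500 or 900 ml, exponential emptying with half-time h of 15 to 120 min, and each meal placed at its midpoint (37.5 and 277.5 min, both eaten in 15 min):

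M(t) = V × 0.5^((t − 37.5)/h), plus V × 0.5^((t − 277.5)/h) from 300 min on.

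Examples at 60 min: 300 × 0.5^(22.5/15) = 106 ml; 900 × 0.5^(22.5/120) = 790 ml.

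| Minute | V=300, h=15 | V=500, h=60 | V=900, h=120 |
|---|---|---|---|
| 0 | 0 | 0 | 0 |
| 60 | 106 | 386 | 790 |
| 120 | 7 | 193 | 559 |
| 180 | 0 | 96 | 395 |
| 240 | 0 | 48 | 279 |
| 300 | 106 | 410 | 988 |
| 360 | 7 | 205 | 699 |
| 420 | 0 | 102 | 494 |

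Relative to the water: 106/150 = 0.7 and 790/150 = 5.3 at 60 min. The excess is clear at 60 and 300 min under every assumption tried. It is probable at 120 and 360 min, and may be negligible by 240 min if emptying is fast.

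**5. Effect on the signal (illustration only).** The documents give no attenuation and no wall displacement. Assuming the signal scales as exp(−μd), with μ from 0.5 to 2 per cm:

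- 2 mm deeper: exp(−0.1) − 1 = −10% to exp(−0.4) − 1 = −33%; 2 mm shallower: +11% to +49%.
- 5 mm deeper: exp(−0.25) − 1 = −22% to exp(−1) − 1 = −63%; 5 mm shallower: +28% to +172%.

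This shows only that a small shift could matter in either direction. It does not estimate a bias in this trial.

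**The case against.** The strongest reply is that the physical chain is not in the documents. They do not say that a full stomach moves the antral wall, or by how much the signal changes with depth, and the fat limit comes without a reason. This stands: the percentages above follow from chosen inputs.

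Second, Section 4 asks whether eating raises the signal enough to mislead the assessment of inflammation, and wants interfering influences mapped. A geometric shift caused by food is one such influence, so the unadjusted contrast still answers that question. This stands too. Only the reading as blood flow is exposed.

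Third, the plan has other measures. Doppler does not depend on antral wall depth, but it is optional and samples large arteries, not the local wall. The normalised spectrum may be less sensitive to a common amplitude factor, but it does not quantify haemoglobin. The dye signal, which Section 4 relies on to tie signal changes to hyperaemia in the segment, does not separate the explanations at the antrum: the chyme that carries the dye also fills the stomach, so the two signals could rise together under either. None of these replaces a depth record.

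Fourth, adjusting for depth is not a clean remedy. Depth is measured after the meal and may track feeding closely in 10 subjects, so adjustment could remove real hyperaemia, and it does not capture wall thinning. This stands and limits the use of the adjusted analysis.

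A reader might go further and infer that any fed–fasting haemoglobin difference is a geometric artefact, or that the primary objective fails. The documents do not support that. The point concerns one of four sites, mainly at the readings soon after a meal. The meal-related excess is zero at the preprandial reading and may be near zero by minute 240, and nothing fixes the direction of any shift.

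**Conclusion.** The concern holds for the antrum at 60 and 300 min, and probably at 120 and 360 min. That filling differs there follows from the plan's own schedule. Its amount, 106 to 790 ml at minute 60, rests on the assumed meal volumes and half-times. That filling matters for the reading is implied by the plan's decision to control it. Because no planned variable separates wall position from haemoglobin content, an antral difference at these times shows that eating changes the signal, but not that blood flow alone is the cause. The size and direction of any geometric part are unknown. In an exploratory pilot this is a limit on interpretation that is worth correcting, not a flaw that defeats the study.

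**What to change.** - **Section 9, Measurement protocol:** reword to say that the water standardises the volume added at each reading and does not equalise filling between fed and fasting arms. No change to the water or the meals is needed.
- **Section 6:** add the depth below the skin of the antral wall region of interest, read from the optoacoustic images already acquired. This assumes skin and wall are both identifiable in those images.
- **Section 10:** at each time point, report the fed–fasting change in antral depth (B versus A, C versus A) beside the haemoglobin change. Give a depth-adjusted analysis as supportive only, not as the rule for calling a difference hyperaemia.
- **Reporting:** where depth shifts with feeding, describe the antral result as a change in optoacoustic signal that may be partly geometric.

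The cost is one distance per antral image, up to 10 subjects × 3 days × 8 readings = 240, and a more cautious antral conclusion. No extra scan, visit or subject is required.

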The regional blood flow in the intestinal wall and the distribution of gastrointestinal blood flow are also subject to strong postprandial changes. During absorption of food components, blood flow increases sequentially in the respective sections of the gastrointestinal tract, leading to postprandial hyperemia. Because postprandial hyperemia is particularly regulated locally by the presence of dietary components, there is a relationship between the sequential increase in blood flow in the intestinal wall and the peristaltic transport of chyme through the gastrointestinal tract. Postprandial hyperemia could also lead to an increase in the optoacoustic hemoglobin signal of the intestinal wall and thus have an impact on the assessment of inflammatory activity in IBD using MSOT. Additionally MSOT allows the identification of non-absorbable exogenous chromophores, such as indocyanine green (ICG), which could allow co-localization of the chyme in the intestinal lumen after oral application of ICG.

The purpose of this pilot study is to investigate in healthy volunteers whether, postprandial blood flow changes can be quantitatively measured using MSOT and whether these changes occur simultaneously with the gastrointestinal passage of the chyme as measured by the ICG signal in the intestinal lumen.

3. Responsibilities

Principle investigator

Dr. med. [name]

Department of Paediatrics and Adolescent Medicine

University Hospital Erlangen

[name]

[name]

[contact]

E-Mail: [contact]

Further investigators

Dr. med. [name]

Department of Paediatrics and Adolescent Medicine

University Hospital Erlangen

[name]

[name]

[contact]

E-Mail: [contact]

[name]

Department of Paediatrics and Adolescent Medicine

University Hospital Erlangen

[name]

[name]

E-Mail: [contact]

[name]

Department of Paediatrics and Adolescent Medicine

University Hospital Erlangen

[name]

[name]

Email: [contact]

Sponsoring

IZKF junior project (J89). Until the start of the project additional internal funds of the Department of Pediatrics and Adolescent Medicine, University Hospital Erlangen.

4. Scientific Background and derivation of the question

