signal of the intestinal wall, resulting in falsely high MSOT signals in the determination of inflammatory activity. Therefore, in this study, influences of a standardized dietary¹⁰ on the MSOT signal of the intestinal wall will be investigated in a longitudinal design and optoacoustic signals will be compared between subjects in fasting and postprandial states. Because the postprandial increase in intestinal blood flow is predominantly a result of the local presence of chyme in the intestine,¹¹ a simultaneous determination of intestinal transit of chyme during MSOT measurement would be helpful to validate whether postprandial changes in MSOT signals are attributable to hyperemia in the corresponding bowel segment. With MSOT, in addition to the determination of hemoglobin, the detection of exogenous chromophores is also possible. Therefore, in this study, oral administration of the nonabsorbable dye ICG will be used for noninvasive identification of the chyme.¹² We believe that the combination of exogenous and endogenous chromophores thus allows accurate co-localization and registration of intestinal wall blood flow patterns and chyme transit. This information enables accurate anatomical mapping of interfering influences on the determination of hemoglobin using MSOT.

The time course of postprandial hyperemia in the different sections of the gastrointestinal tract has been scientifically investigated in many studies. While an increase in blood flow in the stomach and duodenum can be detected after 30-60 minutes, it takes much longer for postprandial hyperemia to be detected in the areas used to measure inflammatory activity with MSOT in IBD such as the terminal ileum and sigmoid colon. An increase in blood flow in the ileum can be measured after 120 minutes at the earliest,¹ and the arrival of chyme in the colon and the accompanying local increase in blood flow occur after approximately 240-300 minutes.^{13,14} Therefore in this study postprandial changes in the MSOT hemoglobin signal will be investigated over period of 7 hours.

Bibliography

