In addition, the study will be terminated for the individual participant if, as a result of adherence to the fasting period before the measurements and during the measurements in study arm A, complaints such as malaise, weakness, a strong feeling of hunger, stomach complaints, abdominal cramps or similar occur.

Termination criteria for the whole study:

A termination of the entire study is not planned

Statement on medical justifiability

Based on previous experience, the risk of undesired events associated with is considered extremely low.

No serious event has been reported so far, neither at our own site nor in literature. The majority of the reported (foreseeable) problems related either to the use of ultrasound gel for examination or the need to wear eye protection. The use of filter glass also explains the reported red-sightedness. This phenomenon was reversible within seconds. Table 1 shows the reported events from our study (MSOT_DMD, 67_18 B, Clinicaltrials.gov Identifier: NCT03490214).

	Muscular dystrophy Duchenne N=10	Healthy volunteer N=10
Reversible adverse events- no.		
Pressure of safety goggles	2 (20%)	
Coolness of Ultrasound-gel		4 (40%)
Red cast view		1 (10%)
Serious adverse events- no.	0 (0%)	0 (0%)

Table 1 – Reported events MSOT_DMD, 67_18 B

The occurrence of adverse side effects from the systemic use of ICG (Verdye, Diagnostic Green 5mg/ml) is very rare (<1 in 10 000). According to the manufacturer, the dye is not absorbed after oral application of ICG and is not subject to enterohepatic circulation. Therefore, the occurrence of systemic side effects from oral intake of ICG is very unlikely.

10. Biometrics

Explorative study: explanation of the statistical methodology, justification of the selected number of cases

Case number calculation:

As this is a pilot study and no information on the expected differences between the different groups is available yet, no case number calculation was performed. The number of cases given represents an estimate or is within the appropriate range for a pilot study.

Statistical methods:

The data is given as mean value with standard deviation. Correlations are given with the non-parametric Spearman correlation coefficient (R_s). According to the distribution on groups the differences of the mean values are examined statically with a nonparametric T-test (Mann-Whitney test) or ANOV. In all analyses an error level of <0.05 is considered statistically significant.

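### The Hb-ICG and Hb-Doppler correlations are planned as plain Spearman tests at 0.05 with no allowance for 7 repeated values per person per day; the person should be the unit, and a positive result read only as shared timing

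*Combined protocol and SAP*

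**What the plan says.** Section 5 lists two correlation objectives, both secondary. Each begins "Correlation between postprandial changes in the oxygenated/deoxygenated hemoglobin signal in the wall of the gastrointestinal tract measured by MSOT"; one pairs those changes with changes in Doppler signals of the splanchnic arteries, the other with changes in the luminal ICG signal on the ICG day. The second serves the purpose given in the introductory summary, to learn "whether these changes occur simultaneously with the gastrointestinal passage of the chyme as measured by the ICG signal in the intestinal lumen". Section 4 gives the reason: "the postprandial increase in intestinal blood flow is predominantly a result of the local presence of chyme in the intestine".

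The data structure is in sections 6 to 9. On numbers: "It is planned to examine a total of 10 study subjects". Each person attends on three days. Each day has one preprandial measurement and one at 60 minutes, after which "further postprandial measurements are taken at 60-minute intervals" up to 7 hours. Section 6 names four bowel segments and three arteries and marks the Doppler targets as optional.

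On analysis, section 10 says "Correlations are given with the non-parametric Spearman correlation coefficient (R_s") and applies a 0.05 significance level to all analyses. It does not state the unit of analysis, define a postprandial change, or say how repeated values from one person, or the segments and fed days, are combined.

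**The concern.** The p-value of a plain Spearman coefficient assumes independent pairs. Here, 70 pairs per segment come from only 10 people. If people differ persistently in both signals, or if one noisy preprandial value is subtracted from all 7 later values in each signal, a pooled R_s can be significant although the signals are unrelated.

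Section 10 shows no sign that within-person dependence was considered: for group differences it names the Mann-Whitney test, which is for independent groups, although every subject passes through all three arms.

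These correlations are the planned evidence on whether wall hemoglobin rises as chyme arrives, and whether it follows arterial flow. An invalid p-value could be read as support for attributing the MSOT change to hyperemia in that segment.

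**Working it through.** The plan gives no power, ICC or error rate beyond the nominal 0.05, so there is no figure to reproduce.

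**Inputs from the documents.** 10 people (section 8); 1 + 6 = 7 postprandial values per day (section 9); 10 × 7 = 70 pairs per segment on the ICG day; level 0.05 (section 10), taken as two-sided.

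**Assumed, because the documents are silent.** ICC, baseline noise, serial correlation, and the shape and timing of any meal response.

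**1. Lasting person effects, pairs pooled, signals unrelated.** With m values per person, the variance of the pooled coefficient is inflated by about 1 + (m − 1) × ICC₁ × ICC₂. The false-positive rate is about 2Φ(−1.96/√inflation).

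| ICC in the two signals | Inflation, m = 7 | Approximate rate | Simulated rate |
|---|---|---|---|
| 0 and 0 | 1 | 5.0% | about 5% |
| 0.3 and 0.3 | 1 + 6 × 0.09 = 1.54 | 11.4% | 10% to 11% |
| 0.5 and 0.5 | 1 + 6 × 0.25 = 2.50 | 21.5% | 19% to 21% |
| 0.7 and 0.7 | 1 + 6 × 0.49 = 3.94 | 32.3% | 31% to 32% |
| 0.7 and 0.3 | 1 + 6 × 0.21 = 2.26 | 19.2% | 17% to 18% |
| 0.5 and 0 | 1 | 5.0% | about 5% |

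The last row matters: if either signal has no person effect, there is no inflation.

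**2. Change from one baseline.** Subtracting the same-day preprandial value removes lasting level differences but puts the same baseline error into all 7 changes. If the baseline SD is k times the later SD, two changes in one person correlate at k²/(1 + k²). Take k = 1 for Hb, giving 0.5. The ICG baseline precedes the dye, so a small k is plausible there.

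| k for ICG | Correlation | Inflation | Approximate rate | Simulated rate |
|---|---|---|---|---|
| 1.0 | 0.500 | 2.50 | 21.5% | 20% |
| 0.7 | 0.329 | 1.99 | 16.4% | 15% |
| 0.5 | 0.200 | 1.60 | 12.1% | 11% |
| 0.3 | 0.083 | 1.25 | 7.9% | 7% |
| 0.1 | 0.010 | 1.03 | 5.3% | 5% |

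**3. The ranges above are not bounds.** Simulated pooled rates are 37% at ICC 0.8 and 43% at ICC 0.9. ICC 0.5 plus first-order serial correlation of 0.3 to 0.7 gives 24% to 35%. Pooling both fed days for Hb-Doppler (140 pairs) gives about 16%, 32% and 47% at ICC 0.3, 0.5 and 0.7.

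**4. R_s within each person, Fisher-z, one-sample t-test on 10 values.** This is significant in about 4% to 6% of runs in the settings of steps 1 and 2, and in 4.6% to 5.1% with serial correlation. Within a day, subtracting or dividing by a positive baseline leaves the ranks unchanged, so the result is the same for raw values, differences and percent changes.

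**5. Limit of step 4.** Everyone eats at the same clock time. Assume a pulse in each signal (height 2.5 noise SD, width SD 1.2 h, mean arrival 4 h), with arrival times drawn independently for the two signals. The per-person test is then significant in about 94%, 77%, 27% to 29% and 10% of runs at arrival SD 0, 0.5, 1.0 and 1.5 h. When the arrivals are truly linked it is significant in 94% to 95%. If transit times are similar, the test cannot tell linked from unlinked signals.

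**6. Removing person and time-point means, then permuting whole-person curves.** This targets a link beyond the common time course and held 4.0% to 5.2% under the null. For linked pulses at the same four arrival SDs, power is 5%, 7%, 18% and about 29% at height 1.5 noise SD, and 5%, 16%, 59% and 83% at height 2.5.

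**7. Second meal.** Arms B and C "receive a standardised breakfast with or without ICG supplement (study arm B/C) 30 minutes after the start of the preprandial measurement". Four hours later, at about 30 + 240 = 270 minutes, they "receive another standardised meal to simulate regular food intake. This meal does not contain ICG". So 3 of the 7 values (300, 360 and 420 minutes) follow a meal that can raise wall hemoglobin without adding ICG.

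**The case against.** The strongest reply is that the plan never says the pairs will be pooled. That stands. A reader might infer that section 10 prescribes an invalid test, but it supports only this much: it names a method that assumes independence, for repeated data, with no safeguard. The Mann-Whitney wording shows that dependence was not addressed; it does not show what an analyst would do.

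Second, the objectives concern changes, so lasting level differences may cancel. This also stands in part. For Hb-ICG, a nearly noise-free ICG baseline brings the pooled rate down to 5% to 7%, unless people also differ persistently in their ICG response. A reader might take about 31% as the size of the problem or its ceiling; it is neither, as step 3 shows.

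Third, the within-person test is itself often significant without a specific link (step 5). This is correct and limits its interpretation. It answers the timing question in the introductory summary. It does not answer the section 5 hypothesis of an association with chyme, or the section 4 aim of attributing change to the corresponding segment.

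Fourth, this is an exploratory pilot, and tests across several segments and arteries would not be confirmatory even if each were valid. That lowers the severity. It does not make a p-value valid when independence fails, and section 10 applies a significance label throughout.

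**Conclusion.** The concern holds as a gap that should be closed before analysis. Plain Spearman at 0.05 makes no allowance for 7 values per person per day. If the pairs are pooled, the p-value is not valid when both signals carry lasting person effects or a shared noisy baseline. The illustrated rates (about 5% to 32% for ICC 0 to 0.7 in both signals; about 5% to 20% from a shared baseline) rest on assumed values, and the true rate could be at nominal or higher than these.

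Two further inferences are not supported. The primary fasting-versus-fed comparison is not touched by this point. And a significant within-person correlation would not by itself show a chyme-specific or artery-specific link. The affected objectives are secondary and exploratory, and the Doppler targets are optional, so this is a recommended change with medium confidence.

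**What to change.** In section 10:

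1. State that the person is the unit of analysis and that no p-values from pooled Spearman will be reported.
2. Per segment (and artery), compute R_s within each person over the postprandial times, Fisher-z transform it (set |R_s| = 1 to 0.99), and test the 10 values against zero. Report the mean R_s with a 95% CI. If both fed days are used for Doppler, average each person's two daily R_s first. An equivalent within-person method, such as repeated-measures correlation, is acceptable; in simulation it held 4.8% to 5.1% for ICC 0 to 0.7, but it was not checked under serial correlation.
3. State that a positive result means shared timing after the meal only.
4. For any claim of a chyme-specific or artery-specific link, also report the analysis with person and time-point means removed and whole-person permutation. State that its power is low when transit times are similar, so a non-significant result is not evidence against a link.
5. State in advance how the Hb-ICG values at 300, 360 and 420 minutes are used, and how missing time points are handled.

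The cost is SAP wording and a few lines of code, with no change to visits or procedures. P-values become less favourable: at ICC 0, the within-person correlation detectable with 80% power rises from about 0.35 (pooled) to about 0.46 (per-person R_s).
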